1.3 DETERMINATION OF SAMPLE SIZE

The sample size is based on the primary efficacy outcome of mean change in BCVA from baseline at Week 24 in the *treatment-naïve patients*. Each RO6867461 dose (Arms B and C) will be compared with the control group (Arm A).

Consider 50 *treatment-naïve* patients randomized to Arms A, B, and C, with a drop-out rate of 10%. Assuming a standard deviation of 11 letters, this sample size

RO6867461—F. Hoffmann-La Roche Ltd

Statistical Analysis Plan BP30099

provides 80% power to detect a true difference of 5 letters at the one-sided α level of 10%. The minimum detectable difference is approximately 3 letters.

Approximately 60 previously IVT anti-VEGF treated patients will be enrolled in addition for exploratory analyses.

1.4 ANALYSIS TIMING

The primary analysis will be performed at the end of the study, after the last patient has completed Week 24 final visit.

2. STUDY CONDUCT

The number of patients who are enrolled, discontinued, and completed the study will be summarized as well as the major protocol violations. Demographic and other baseline characteristics will be summarized with descriptive statistics.

2.1 RANDOMIZATION

After written informed consent has been obtained, all patients will receive a screening number assigned through the Interactive Voice and Web Response System (IxRS). After all patient eligibility requirements are confirmed on Day 1 visit the site personnel will contact the IxRS for assignment of a patient identification number (a separate number from the screening number).

Approximately 50 treatment-naïve patients will be randomized on each arm (1:1:1 randomization scheme) and approximately 30 patients previously treated with IVT anti-VEGF will be randomized into arms A and C. Randomization will be stratified for the three factors below:

- Baseline BCVA ETDRS letter score assessed on Day 1 (64 letters or better vs. 63 letters or worse)
- Previous Macular Laser treatment (Yes/No)

Previous IVT anti-VEGF treatment in study eye (Yes/No)

2.2 INDEPENDENT REVIEW FACILITY

A Roche internal monitoring committee (IMC) will be responsible in the event of an interim analysis for sample size evaluation, operational/administrative purposes, and/or for safety data monitoring. For other objectives, the IMC will review the safety data and will be responsible for evaluating efficacy data for instance where assessment of benefit-risk is warranted. These analyses will take place at pre-defined time points or on an ad-hoc basis.

The IMC consists of a selected subset of Roche representatives including a biostatistician, safety representative, clinical science representative, clinical pharmacology representative, and pharmacometrist. The IMC members participating in a given interim analysis will be kept to the minimum required to address the objective of that interim analysis. Additional Roche Representatives might be involved to produce/process the unmasked listing/data to be analyzed by the IMC.

RO6867461—F. Hoffmann-La Roche Ltd
Statistical Analysis Plan BP30099

Full details regarding the IMC will be provided separately in the IMC agreement.

2.3 DATA MONITORING

An IMC will review safety data, and may review efficacy data to assess benefit-risk.

3. STATISTICAL METHODS

3.1 ANALYSIS POPULATIONS

The following analysis populations will be defined: "Efficacy, Pharmacokinetic, and Pharmacodynamic Population" and safety population.

3.1.1 Safety Analysis Population

All patients who have received at least one dose of the study drug, whether prematurely withdrawn from the study or not, will be included in the safety analysis. Patients will be grouped according to the actual treatment received.

3.1.2 Efficacy, Pharmacokinetic, and Pharmacodynamic Population

All randomized patients (Intent to Treat, ITT) will be included in the efficacy, PK, and PD analysis population. Patients who receive study drug in the study eye different than to which they were randomized will be included in the group to which they were randomized. Separate ITT populations for the treatment-naïve and previously anti-VEGF-treated patients will be defined.

3.2 ANALYSIS OF STUDY CONDUCT

The number of patients who are enrolled, discontinued, and completed the study as well as the major protocol violations will be summarized. Demographic and baseline characteristics will be summarized with descriptive statistics by previous anti-VEGF treatment status.

3.3 ANALYSIS OF TREATMENT GROUP COMPARABILITY

Demographics, baseline characteristics (including ocular assessments, patient disposition, and medical history), and all baseline laboratory values will be summarized descriptively by treatment arm and previous anti-VEGF treatment status using frequency tables and summary statistics providing means, medians, standard deviations, first and third quartiles, and extreme values.

3.4 GENERAL CONSIDERATIONS

3.4.1 Visit Windows

Visit windowing will be performed for this study with nominal visits/assessments falling outside of allowable protocol-defined visit windows, being reassigned to an appropriate visit for use in analyses.

If multiple valid (non-missing) values for a variable are recorded in the same visit window, one record will be selected for summary/analysis of the data by the following priority:

- The originally scheduled visit assessment

- The assessment closest to the target/planned assessment day.

If scheduled assessments were grouped into multiple visits, the assessments will be assigned to a single visit provided all assessments fall within the same visit window.

Note that unscheduled visits could potentially be included in summaries and analyses following the application of these visit assignment rules.

Assessments that fall outside of the protocol-defined visit windows will be assigned to the closest target visit.

Unless otherwise specified, all analyses and summaries involving visit, will use visits assigned after visit windowing has been performed.

3.4.2 **Baseline**

The baseline measurement is the latest non-missing observation before the first dose of study medication.

3.5 **EFFICACY ANALYSIS**

The List of Planned Outputs (LoPO) contains the full list of reports for the efficacy analysis.

The primary and secondary efficacy analyses will include all randomized treatment-naïve patients, with patients grouped according to the treatment assigned at randomization. Patients with previous IVT anti-VEGF will be analyzed separately. Unless there is strong evidence for RO6867461 effect modification by previous IVT anti-VEGF, primary efficacy analyses will be repeated in all randomized patients (see 3.5.3).

3.5.1 **Primary Efficacy Endpoint**

The primary efficacy variable is the study eye BCVA change from baseline at Week 24. The primary efficacy analysis will be performed using a Linear Mixed Effects Model for Repeated Measurements (MMRM) model. The model will include the categorical covariates of treatment group, categorical visit, and visit by treatment group interaction term, randomization stratification factors, and a continuous covariate of baseline BCVA. An unstructured covariance will be used to account for within-patient correlation (General Linear Model), but another variance-covariance structure such as AR(1) + random patient effect may be selected in case of convergence issues. The primary statistical test will aim to test the null hypothesis:

H_0 : There is no difference between either of the RO6867461 arms (Arms B and C) and the control group (Arm A) for mean BCVA change from baseline at Week 24 in the treatment-naïve patient population vs.

H_A : Arm B or C is different from arm A.

The model-based estimate of the difference between each of the treatment groups (Arms B and C) and the control group (Arm A) at Week 24, together with 80% confidence interval and corresponding p-value will be reported as the primary

efficacy measures. The mean and 80% CI within each treatment group and for the difference between RO6867461 treatment groups (Arms B and C) and the control group (Arm A) at the other time points will also be reported. There will be no formal correction for multiple comparisons. Tests for arms B vs A and C vs A will be carried out at one-sided 10% alpha.

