4.3.1.1 Criteria for Treatment with Ranibizumab during Observational Period

At each visit following the last dose of study treatment (week 20 visit), BCVA will be assessed and SD-OCT imaging will be performed (except for week 26 visit).

BCVA and CST values obtained at week 24 will be compared to those obtained at visit week 20. BCVA and CST values obtained at weeks 28, 32 and 36 will be compared to those of week 24.

If the patient meets both of the following criteria the patient should receive a single dose of 0.3 mg ranibizumab and will exit the study:-

- CST increased by $\geq 50 \mu\text{m}$
- BCVA decreased by ≥ 5 letters due to DME

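### On the visible text, the SAP visit-window rule relabels a Week 24 BCVA taken 8 to 20 days late as Week 26, moving a measured primary value off the primary time point

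*SAP*

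**What the plan says.** SAP 3.4.1 (Visit Windows) begins in general terms, with "nominal visits/assessments falling outside of allowable protocol-defined visit windows, being reassigned to an appropriate visit for use in analyses". It then gives the operative rule: "Assessments that fall outside of the protocol-defined visit windows will be assigned to the closest target visit". It adds that, unless otherwise specified, "all analyses and summaries involving visit, will use visits assigned after visit windowing has been performed".

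The same section ranks competing records, giving first place to the visit as originally scheduled and second to the assessment nearest the planned day. That ranking has a condition: "If multiple valid (non-missing) values for a variable are recorded in the same visit window, one record will be selected".

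The schedule (SAP Appendix 2; Protocol Appendix 1) puts Week 20 at Day 140, Week 24 at Day 168, Week 26 at Day 182 and Week 28 at Day 196. Each has a window of 7 days either side. BCVA is marked at all four visits. SD-OCT and angiography are not marked at Week 26, and Protocol 4.3.1.1 agrees on imaging after the last dose: "BCVA will be assessed and SD-OCT imaging will be performed (except for week 26 visit". The Week 26 column carries footnote m, which is redacted.

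SAP 3.5.1 defines the endpoint: "The primary efficacy variable is the study eye BCVA change from baseline at Week 24". It is analysed by MMRM with visit as a categorical term. SAP 3.7 assumes missing at random, with LOCF as a sensitivity analysis.

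The SAP has no window table by variable, no tie rule and no list of the visits that enter the MMRM.

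**The concern.** Visits in this part of the trial run every four weeks, except that Week 26 sits halfway between Weeks 24 and 28. A nearest-target rule puts the boundary between two visits at their midpoint. After Week 24 that boundary is only 7 days away, because the next target is Week 26. Before Week 24 it is 14 days away, because the previous target is Week 20.

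A patient who attends the Week 24 visit late, and has BCVA measured, can therefore have no Week 24 value in the primary analysis. MMRM can use the relabelled value through the within-patient covariance only if Week 26 is a model visit, which the SAP does not say. If LOCF is run on the windowed visits, it would usually carry the Week 20 value forward in place of the later measurement.

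Secondary endpoints may be touched too. If target visits are not specific to each variable, late SD-OCT and angiography results move to a visit at which they are not scheduled.

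**Working it through.** **1. The plan's own figure.** Inputs from SAP 1.3: 50 treatment-naïve patients per arm, 10% drop-out (45 evaluable per arm), "Assuming a standard deviation of 11 letters", and 80% "power to detect a true difference of 5 letters at the one-sided α level of 10"%.

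- Standard error = 11 × √(2/45) = 2.319.
- Power = Φ(5/2.319 − 1.282) = Φ(0.875) = 80.9%, which reproduces the stated 80%.
- Minimum detectable difference = 1.282 × 2.319 = 2.97 letters, which reproduces the stated figure of about 3.

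**2. Where a nominal Week 24 visit goes.** The visit stays at Week 24 if it falls on Day 161 to 175. Otherwise it takes the smallest distance to Days 140, 168, 182 and 196.

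| Timing against Day 168 | Day | Distance to the competing targets | Assigned to |
|---|---|---|---|
| 15 days early | 153 | Week 20: 13; Week 24: 15 | Week 20 |
| 14 days early | 154 | Week 20: 14; Week 24: 14 | tie |
| 8 to 13 days early | 155–160 | Week 24 is nearest | Week 24 |
| up to 7 days either way | 161–175 | inside its own window | Week 24 |
| 8 days late | 176 | Week 24: 8; Week 26: 6 | Week 26 |
| 20 days late | 188 | Week 26: 6; Week 28: 8 | Week 26 |
| 21 days late | 189 | Week 26: 7; Week 28: 7 | tie |
| 22 days late | 190 | Week 26: 8; Week 28: 6 | Week 28 |

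With Week 26 removed from the targets, 8 to 13 days late (Day 176 to 181) stays at Week 24. Day 182 is a tie between Weeks 24 and 28, and Day 183 onward goes to Week 28.

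**3. Does the priority list prevent this?** No. It chooses among several values already in one window. A single late value is relabelled first, so there is nothing to choose between at Week 24. If the patient also has a scheduled Week 26 BCVA, the list favours that record and the late Week 24 value is the one dropped.

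**4. How many patients.** The documents give no data on visit timing. Assume actual timing is normal around Day 168 with SD s, and count visits at least 8 days late as P(Z > 7.5/s). The base is 150 × 0.90 = 135, because drop-outs have no Week 24 visit. Power uses 45 × (1 − share) per arm in the formula of step 1.

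| Assumed SD (days) | Share 8+ days late | Patients of 135 | Evaluable per arm | Power |
|---|---|---|---|---|
| none lost | 0% | 0 | 45.0 | 80.9% |
| 3 | 0.6% | 0.8 | 44.7 | 80.7% |
| 4 | 3.0% | 4.1 | 43.6 | 80.0% |
| 5 | 6.7% | 9.0 | 42.0 | 78.9% |

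The largest loss is 80.9 − 78.9 = 2.0 points. The formula treats each affected value as wholly lost and ignores what MMRM recovers from other visits.

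For the early side at SD 5, P(Z < −14.5/5) = 0.0019, or about 0.25 of 135 patients. That compares with 9.0 on the late side.

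**The case against.** The strongest objection is that Week 26 may not be a general visit. Its footnote is redacted, the text describes observational evaluations as four-weekly, and Protocol 4.3.1.1 compares only Weeks 24, 28, 32 and 36 against earlier values. If Week 26 is not a target visit for BCVA, Day 176 is nearest to Week 24 and the problem disappears. This stands as a condition on the finding. It does not remove it, because the visible schedule marks BCVA at Week 26 for all and the windowing rule does not depend on whether the patient was due there.

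A reader might infer that the rule loses late visits only, or that every affected value is discarded. Neither follows. Visits 15 or more days early also leave Week 24. The late value is kept under a Week 26 label unless a scheduled Week 26 BCVA displaces it, and another record, including an unscheduled one, may be windowed into Week 24.

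A reader might also infer that CST values are certainly stranded. SAP 3.4.1 speaks of an appropriate visit and selects records by variable, so a reading in which Week 26 is no target for SD-OCT is natural. On that reading CST stays at Week 24 while BCVA from the same attendance moves to Week 26. The text does not settle which reading is meant.

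Finally, assigning by actual day is a defensible convention, and the effect on power is small. Both points stand. They limit the weight of the finding, but do not show that this result for Week 24 was intended.

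**Conclusion.** The point holds on the visible text as a low-cost improvement to the SAP. Applied as written, the rule moves a nominal Week 24 BCVA taken on Day 176 to 188 to Week 26, leaves Day 189 undetermined, and sends later visits to Week 28. The threshold is 8 days on the late side and 15 on the early side.

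The size is modest: about 1, 4 or 9 of 135 patients, and at most about 2 points of power. This rests on assumed timing SDs of 3 to 5 days. An SD of 5 already implies about 13% of Week 24 visits outside the protocol's own window, counting both tails (2 × 6.7%).

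The documents do not support reading this as a serious loss of power or as a bias between arms. All arms share one schedule under masking, and nothing shows that lateness would differ by arm. The conclusion also depends on Week 26 being a BCVA target visit, which the redacted footnote could qualify.

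**What to change.** In SAP 3.4.1, state that Week 26 is not a target visit for reassigning out-of-window assessments, and that only assessments recorded as the scheduled Week 26 visit carry that label. A nominal Week 24 assessment then stays at Week 24 up to the midpoint with Week 28. Add that a tie on Day 182 goes to the nominal visit. Applying the sentence to all variables also settles the SD-OCT and angiography question.

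This changes analysis labels only, not the visit schedule, and should be settled before unmasking so that the windows cannot appear to be chosen from the data. The cost is about one sentence and a real trade-off: a few Week 24 values will be up to 14 days late, and so further from the last dose at Week 20.

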4.3 METHOD OF TREATMENT ASSIGNMENT AND MASKING

4.3.1 Treatment Assignment

After written informed consent has been obtained, all patients will receive a screening number assigned through the interactive voice and web response system (IxRS).

A patient must satisfy all eligibility criteria (see Section 4.2.1 and Section 4.2.2) at the screening or Day 1 visit (as defined for each individual criterion in Section 4.2 and below) prior to randomization and first study treatment (see Section 4.6.7.1). As part of the screening process, FP, FFA, and SD-OCT will be transferred to the central reading center, and a set of images will be evaluated to provide an objective, masked assessment of certain eligibility criteria.

Only one eye will be selected as the study eye. See Section 4.6.7.1 for details.

After all patient eligibility requirements are confirmed on Day 1 visit (see Section 4.2), including:

- Baseline BCVA letter score of 73 to 24 letters (inclusive) in the study eye
- Absence of active intraocular inflammation in the study eye
- Absence of febrile illness within one week prior to Day 1,

the site personnel will contact the IxRS for assignment of a patient identification number (a separate number from the screening number).

Treatment naïve patients will be randomized in a 1:1:1 ratio to one of the arms A, B and C, respectively. Patients previously treated with IVT anti-VEGF will be randomized in a 1:1 ratio to arms A and C.:

- Arm A: 0.3 mg ranibizumab IVT
- Arm B: 1.5 mg RO6867461 IVT

RO6867461—F. Hoffmann-La Roche Ltd
37/Protocol BP30099, Version 3

- Arm C: 6 mg RO6867461 IVT

This study will consist of a treatment period (20 weeks) and an observational period (up to 16 weeks), for a total study length of up to 36 weeks. During the treatment period, the study drug will be administered to the patients on Day 1 and on every 4th week, for a total of 6 injections. During the observational period, patients will be evaluated every 4th week. If during any of these evaluations the patients meet the pre-specified criteria (see Section 4.3.1.1), the patients will receive a single dose of 0.3 mg ranibizumab and exit the study. They will receive a follow up phone call 7 days after the dose of ranibizumab to evaluate any potential adverse events. Otherwise, patients will exit the study once they have completed the observational visit at week 36.

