6.7 EFFICACY ANALYSES

The primary and secondary efficacy analyses will include all randomized *treatment-naïve* patients, with patients grouped according to the treatment assigned at randomization. *Patients with previous IVT anti-VEGF will be analyzed separately. Unless there is strong evidence for RO6867461 effect modification by previous IVT anti-VEGF, analyses will be repeated in all randomized patients.*

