3.5.3 Exploratory Efficacy Endpoints

Time to event endpoints will be tested with a two-sided stratified log rank test using the randomization stratification factors BCVA ETDRS letter score (64 letters or better vs. 63 letters or worse) and previous macular laser treatment as strata. Kaplan Meier curves will be displayed, and median time to event estimates will be computed.

Effect modification will be tested in the overall (treatment-naïve and previously treated combined) ITT population by adding a previous IVT anti-VEGF treatment status and a treatment arm by visit by previous IVT anti-VEGF treatment status interaction terms to the Linear model described in section 3.5.1. The treatment arm by visit by previous IVT anti-VEGF treatment status interaction term will be tested at a 10% significance level.

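### The default pooled repeat includes B vs A although Arm B has no previously treated patients; without a status-by-visit term that supportive contrast can be biased

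*SAP*

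**What the plan says.** Treatment-naive patients are randomised 1:1:1 to A, B and C. For the others, Protocol 4.3.1 states: "Patients previously treated with IVT anti-VEGF will be randomized in a 1:1 ratio to arms A and C". SAP 1.3 gives their number and purpose: "Approximately 60 previously IVT anti-VEGF treated patients will be enrolled in addition for exploratory analyses".

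The primary population is treatment-naive. SAP 3.5 then adds a repeat that goes ahead by default: "Unless there is strong evidence for RO6867461 effect modification by previous IVT anti-VEGF, primary efficacy analyses will be repeated in all randomized patients". Protocol 6.7 has the same rule without the restriction to primary analyses: barring strong evidence of "effect modification by previous IVT anti-VEGF, analyses will be repeated in all randomized patients".

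SAP 3.5.1 defines what is repeated: "Tests for arms B vs A and C vs A will be carried out at one-sided 10% alpha". Its model has treatment, visit, treatment by visit, "randomization stratification factors, and a continuous covariate of baseline BCVA". SAP 2.1 lists previous anti-VEGF treatment of the study eye among those factors. For the effect-modification test, SAP 3.5.3 speaks of "adding a previous IVT anti-VEGF treatment status and a treatment arm by visit by previous IVT anti-VEGF treatment status interaction terms" to the 3.5.1 model. No text drops B vs A from the pooled repeat.

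**The concern.** In the pooled set, Arms A and C mix two kinds of patient and Arm B contains one. Pooled B vs A is therefore not a fully randomised comparison; it depends on the model to remove the effect of status. A single status coefficient can remove only a difference that is the same at every visit. Patients treated before may follow a different BCVA course from naive patients, and nothing in the plan makes that difference constant over time.

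The condition for the repeat does not protect this contrast. It asks whether the drug effect differs by status. The bias needs only that status is prognostic, with no effect modification at all. Effect modification for the 1.5 mg dose cannot be examined in any case, because Arm B has no previously treated patients.

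At stake is one estimate, with its confidence interval and p-value, that will be produced by default. If previously treated patients gain fewer letters, it leans towards the 1.5 mg dose without a drug effect; if they gain more, it leans against.

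**Working it through.** **1. The plan's own figure.** SAP 1.3: 50 naive patients per arm, 10% drop-out, SD 11, difference 5 letters, one-sided 10%. Completers 45 per arm; SE = 11 × √(2/45) = 2.32. Power = Φ(5/2.32 − 1.2816) = 0.809; minimum detectable difference = 1.2816 × 2.32 = 2.97. Both stated figures (80%, about 3 letters) are reproduced.

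**2. Mix.** A = 50 + 30, B = 50 + 0, C = 50 + 30. Share previously treated: 30/80 = 37.5% in A and C, 0% in B. After 10% drop-out: 45 + 27, 45, 45 + 27, and 27/72 is again 0.375.

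**3. Bias formula.** Assume no drug effect, and that previously treated patients gain d(v) fewer letters than naive patients at visit v. With free arm-by-visit means and one status coefficient, that coefficient estimates g, an average of d(v) over visits weighted by the inverse covariance matrix. Then

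bias of B − A at Week 24 = 0.375 × (d(24) − g).

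If d(v) is constant, g = d(24), the bias is 0 and the error rate is 10.0%.

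**4. One case by hand.** Visits at Weeks 1, 4, 8, 12, 16, 20, 24; linear build-up to d; SD 11 throughout; exchangeable correlation 0.6 (equal weights).
- g = d × (85/7)/24 = 0.506d, so bias = 0.375 × 0.494d = 0.185d, or 0.93 letters at d = 5.
- Information on status within A and C: 2 × 45 × 27/72 = 33.75. SE = 11 × √(1/72 + 1/45 + 0.375² × (4.6/7)/33.75) = 2.17.
- Error = 1 − Φ(1.2816 − 0.93/2.17) = 19.6%.

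**5. Range.** Four building courses (linear; 1 − exp(−t/τ) with τ = 4, 8, 12 weeks, scaled to 1 at Week 24) and five correlation structures (exchangeable 0.6 and 0.8; autoregressive 0.8 and 0.9 per 4 weeks; random patient effect 0.5 plus autoregressive 0.7). SD 11 at every visit, Weeks 1–24:

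| d at Week 24 (letters) | Bias towards B (letters) | Error of one-sided 10% test |
|---|---|---|
| 1 | 0.07–0.19 | 10.6%–11.6% |
| 2 | 0.14–0.37 | 11.2%–13.3% |
| 4 | 0.29–0.74 | 12.5%–17.4% |
| 5 | 0.36–0.93 | 13.2%–19.6% |

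For d = 1 to 5, other visit sets give somewhat less: Weeks 4–24, 0.04–0.78 letters and 10.3%–17.9%; Weeks 1–36, 0.05–0.80 letters and 10.4%–18.1%. If previously treated patients gain more, the sign reverses and the error falls to 4.4%–9.7%.

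**6. The SD assumption matters.** The plan gives SD 11 only for the Week 24 sample size, and the unstructured covariance allows unequal variances. If the SD rises from 8 or 6 to 11 over Weeks 1–24 (assumed), the bias is 0.17d to 0.53d: at d = 5, up to about 2.7 letters with an error near 49%. Above 0.375d, g has the wrong sign and the adjustment does worse than none.

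**7. Protocol model.** Protocol 6.7.1 lists no stratification factors. Pooled B vs A would then carry the full 0.375d: 0.4 letters at d = 1, 1.9 at d = 5.

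**8. Alternatives.**
- Status crossed with visit: bias 0 if there is no effect modification; SE = 11 × √(1/72 + 1/45 + 0.375²/33.75) = 2.21.
- B vs A in naive patients only: bias 0, SE 2.32.
- Pooled C vs A: bias 0 in every scenario, because A and C have the same mix; SE = 11 × √(2/72) = 1.83.

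**9. Power of the condition.** Treated as a single Week 24 contrast, the A–C interaction has SE = 11 × √(2/45 + 2/27) = 3.79. Power at two-sided 10% is about 20% for a 3-letter modification and 37% for 5 letters. A missed modification of m letters shifts pooled B vs A by 0.375 × m/2, or 0.56 and 0.94 letters. A status-by-visit term does not remove that shift.

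**The case against.** The strongest reply is that little depends on this contrast. The primary population, null hypothesis and sample size are all treatment-naive, the previously treated patients are there for exploration, and the randomised naive B vs A is reported alongside. That stands, and it limits the point to minor.

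Second, the SAP already adjusts for status, and a constant status effect leaves no bias. That is correct. The bias needs a status difference that changes over visits, on which the documents are silent, so its existence and size are conditional.

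Third, the SAP 3.5 sentence ends by referring to 3.5.3. If the 3.5.3 model were the model for the repeat, its three-way term would, under usual coding, cover status by visit and the mechanism above would disappear. The reference more naturally points to the effect-modification test. On the other reading the problem changes but does not go away: the cell for previously treated patients in Arm B is empty, so B vs A averaged over status cannot be estimated.

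Fourth, the list of planned outputs is not available, so it cannot be confirmed that a pooled B vs A table will be produced. What can be said is that the SAP text calls for it and does not exclude it.

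**Conclusion.** The concern holds, as a minor point about a supportive analysis. Followed as written, the pooled repeat compares B with A although the two arms differ by design in previous treatment, and the model removes only the part of a status effect that is constant over visits.

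Under a constant SD of 11 the bias stays below 1 letter for status differences up to 5 letters, small beside the 5-letter design difference. It can still nearly double the nominal 10% error at the upper end. That description rests on the constant SD: with smaller early variances, or with the Protocol 6.7.1 model, the bias is larger. The logic is certain; the size is not, because the documents give neither a status effect nor its time course. Naive B vs A and pooled C vs A are free of this bias.

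**What to change.** State in SAP 3.5 and Protocol 6.7 that the repeat in all randomised patients reports C vs A only, and that B vs A is reported in treatment-naive patients only. This removes the bias under either document's model. It needs no patients or data. B vs A keeps SE 2.32 letters instead of 2.21, about 5% more, while C vs A keeps its gain from pooling (2.32 to 1.83, about 21% less).

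If Arm B is to stay in the pooled model, list status and status by visit for the pooled run in SAP 3.5.1, and bring Protocol 6.7.1 into line. Say in SAP 3.5.3 that status is already in the model, since the present wording adds it a second time, and state that pooled B vs A then assumes no effect modification.

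A separate clerical point: the primary-analysis sentence in the Protocol synopsis and in SAP Appendix 1 refers to all randomised patients and should name the treatment-naive ones, as the same synopses do elsewhere.
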